APPENDIX J. PROTOCOL SUMMARY OF CHANGES

Previous Protocol Versions

Protocol	Date
Version 1.0	07 May 2020
Version 2.0	31 October 2020
Version 3.0	17 February 2022
Administrative Change 1	12 July 2022
Version 4.0	04 January 2023

The purpose of this version is to correct clerical errors for consistency throughout the protocol and incorporate necessary protocol modifications, including those outlined as follows:

- The list of signatories in [Appendix C](#) was updated.
- In [Appendix E](#) and [Appendix K](#) requirements for PET scans during response assessments and scheduled follow-up visits were removed reflect that primary analysis was completed and further IRC assessment will not be conducted.
- [Appendix G](#) replaced hypocalcemia classification for lab TLS from "Corrected calcium < .75 mg/dL (1.75 mmol/liter) or ionized calcium < 1.12 mg/dL (0.03 mmol/liter)" to "Corrected calcium < 7.0 mg/dL (1.75 mmol/liter) or ionized calcium < 4.5 mg/dL (1.12 mmol/liter)" to align with the review article from which the value was cited.³⁸
- The SAE reporting fax numbers in [Appendix K](#) were updated.

1.0 Introduction

This Statistical Analysis Plan (SAP) describes the statistical analyses for venetoclax Study M20-075: "Phase 2 Study of the Efficacy and Safety of Venetoclax in Combination with Ibrutinib in Japanese Subjects with Relapsed/Refractory Mantle Cell Lymphoma," protocol amendment 3.0 dated February 17, 2022.

Study M20-075 examines the efficacy and safety of venetoclax and ibrutinib in subjects with relapsed/refractory (R/R) mantle cell lymphoma (MCL).

The SAP will not be updated in case of administrative changes or amendments to the protocol unless the changes impact the analysis.

Unless noted otherwise, all analyses will be performed using SAS Version 9.4 (SAS Institute Inc., Cary, NC 27513) or later under the UNIX operating system.

2.0 Study Design and Objectives

2.1 Objectives, Hypotheses and Estimands

The primary objective of the study is to evaluate the effect on best overall response of complete response (CR) of the concurrent administration of venetoclax and ibrutinib in Japanese subjects with R/R MCL.

The hypothesis corresponding to the primary objective is to demonstrate superiority of venetoclax in combination with ibrutinib against a historical reference of 12.5% complete response rate (CRR) in Japanese subjects with R/R MCL treated with ibrutinib only.

The estimand corresponding to the primary objective is:

Proportion of best overall response of CR as assessed by IRC, for subjects receiving venetoclax in combination with ibrutinib (with approximately 104 weeks on combination therapy, followed by ibrutinib monotherapy until disease progression [PD]), regardless of

whether or not the subject is receiving study drugs and regardless the use of other anti-MCL treatments, in the R/R MCL subjects.

The secondary objectives of the study are:

- To evaluate the effect on best overall response of CR or partial response (PR), duration of response (DOR), MRD, PFS, and OS of the concurrent administration of venetoclax and ibrutinib in Japanese subjects with R/R MCL.
- To evaluate the safety and tolerability of the concurrent administration of venetoclax and ibrutinib in Japanese subjects with R/R MCL.
- To evaluate the pharmacokinetics of venetoclax and ibrutinib in Japanese subjects with R/R MCL.

Hypotheses corresponding to the secondary objectives, are to achieve positive results with venetoclax in combination with ibrutinib (i.e., greater proportion of subjects achieving favorable outcomes or longer duration of positive benefits, etc.).

The estimands corresponding to the secondary objectives are:

- Proportion of subjects achieving:
 - Best overall response of CR or PR (as assessed by Independent Review Committee [IRC]/investigator)
 - Best overall response of CR (as assessed by investigator)
 - Undetectable MRD (disease assessed by IRC/investigator)
With venetoclax in combination with ibrutinib (with approximately 104 weeks on combination therapy, followed by ibrutinib monotherapy until PD), regardless of whether or not the subject is receiving study drugs and regardless of the use of other anti-MCL treatments, in the R/R MCL subjects.
- The median time-to-event (if estimable) will be estimated for the following endpoints:
 - Duration of response (as assessed by IRC/investigator)
 - PFS (as assessed by investigator)

- OS
 - with venetoclax in combination with ibrutinib (with approximately 104 weeks on combination therapy, followed by ibrutinib monotherapy until PD), regardless of whether or not the subject is receiving study drugs and regardless of the use of other anti-MCL treatments, in the R/R MCL subjects.

2.2 Study Design Overview

This Phase 2, open-label, single-arm study is designed to evaluate the efficacy and safety of the combination of venetoclax and ibrutinib in Japanese subjects with R/R MCL.

Approximately 12 subjects will receive ibrutinib at 560 mg once daily until progression and venetoclax starting at 20 mg once daily and gradually ramped up to a target dose of 400 mg once daily over a 5-week period for a maximum period of 104 weeks.

[figure not shown]
Dose-limiting toxicities will be evaluated in the first 6 subjects, from Day 1 for a minimum of 5 weeks and at least 1 week of venetoclax dosing at 400 mg, in order to confirm the initial safety and tolerability in Japanese subjects. After the completion of the DLT evaluation period in the first 6 subjects, the AbbVie Study Team and investigators who enrolled the 6 treated subjects will review all available safety and PK data to evaluate the tolerability of venetoclax in combination with ibrutinib in Japanese subjects with R/R MCL. If there are zero or 1 DLTs in the first 6 subjects, enrollment of the additional 6 subjects will proceed. If DLTs are observed in 2 or more of the first 6 subjects, further enrollment in Japan will be interrupted and additional, a detailed safety assessment will be conducted.

A DLT is defined as any Grade ≥ 3 adverse events considered to be at least possibly related to study drug (ibrutinib and/or venetoclax) and occurring during the DLT assessment period as defined in protocol Section 6.3. Under certain circumstances as defined in protocol Section 6.3, a subject is not evaluable for DLT, that subject will be replaced but are included for efficacy analysis.

Subjects who discontinue study treatment for any reason will be followed for progression (if no progression before treatment discontinuation), subsequent anti-cancer therapy, and survival status until study closure, as appropriate

The schematic of the study is shown in [Figure 1](#).

Figure 1. Study Schematic

FU = follow up; MCL = mantle cell lymphoma; PD = disease progression; R/R = relapsed/refractory; wks = weeks

Note: After approval of venetoclax and ibrutinib combination therapy for R/R MCL in Japan, Study M20-075 will be discontinued, and subjects will transition to commercial drug.

2.3 Treatment Assignment and Blinding

The treatment is venetoclax in combination with ibrutinib for up to 104 weeks starting Week 1 Day 1. Venetoclax will discontinued after a maximum of 104 weeks of treatment followed by ibrutinib monotherapy until PD. The study will be discontinued after approval of the venetoclax and ibrutinib combination for R/R MCL in Japan and subjects continuing to derive benefit at that time will transition to commercial supplies.

As this is an open label study, so blinding is not applicable.

2.4 Sample Size Determination

Approximately 12 subjects will be enrolled in the study. The tolerability of the combination of venetoclax and ibrutinib will be assessed after the first 6 subjects enrolled

in the study have received the combination for a minimum of 5 weeks and at least 1 week of venetoclax dosed at 400 mg.

Using exact binomial test, with an expected complete response rate (CRR) of 50% for venetoclax in combination with ibrutinib and a threshold CRR of 12.5%, 12 subjects will provide 80% power to demonstrate superiority of venetoclax in combination with ibrutinib against a historical reference of 12.5% CRR in the ibrutinib only Japanese study with R/R MCL, at a 1-sided overall significance level of 0.025. A significant test result is achieved when at least 5 CRs are observed among 12 subjects, corresponding to a minimal observed CRR of 41.7%.

If the first 12 subjects include one or more subjects who are assessed by the IRC as non-evaluable at baseline, then additional subject(s) will be enrolled at the Sponsor's discretion to ensure that there are 12 evaluable subjects per IRC assessment for primary endpoint analysis.

3.0 Endpoints

3.1 Primary Endpoint

The primary endpoint is best overall response of CR according to the Revised Criteria for Response Assessment (Cheson 2014)¹ as assessed by the Independent Review Committee (IRC). The best overall response of CR is defined as achieving an overall response of CR at any time point during the study.

3.2 Secondary Endpoints

The secondary efficacy endpoints are listed below:

- Investigator-assessed best overall response of CR, according to the Revised Criteria for Response Assessment (Cheson 2014).¹
- IRC-assessed best overall response of CR or PR (defined as achieving partial metabolic and/or radiologic response at any time point during the study according to the Revised Criteria for Response Assessment (Cheson 2014).¹

- Investigator-assessed best overall response of CR or PR, according to the Revised Criteria for Response Assessment (Cheson 2014).¹
- Investigator-assessed DOR, defined for subjects who achieve a best overall response, as the time from the first occurrence of response to disease progression or death, whichever occurs first, according to the Revised Criteria for Response Assessment (Cheson 2014).¹
- IRC-assessed DOR, defined for subjects who achieve a best overall response, as the time from the first occurrence of response to disease progression or death, whichever occurs first, according to the Revised Criteria for Response Assessment (Cheson 2014).¹
- Undetectable MRD in subjects who achieve a best overall response of CR as assessed by investigator, according to the Revised Criteria for Response Assessment (Cheson 2014).¹
- Undetectable MRD in subjects who achieve a best overall response of CR as assessed by IRC, according to the Revised Criteria for Response Assessment (Cheson 2014).¹
- Progression-free survival (PFS), defined as the time from the date of the first dose of any study drug (venetoclax or ibrutinib) to the date of investigator-assessed disease progression, using the Revised Response Criteria for Response Assessment (Cheson 2014),¹ or death from any cause, whichever occurs first.
- Overall Survival, defined as the time from the date of the first dose of any study drug (venetoclax or ibrutinib) to death from any cause.

3.3 Other Efficacy Endpoints

Not applicable.

3.4 Safety Endpoints

Safety and tolerability will be assessed by evaluating DLTs, adverse events, physical examinations, and changes in laboratory data (hematology, chemistry, and urinalysis) and vital signs for the entire study treatment duration.

3.5 Pharmacokinetic Endpoints

Intensive blood samples for analysis of venetoclax and ibrutinib PK will be collected at Week 6 Day 1. Values for the pharmacokinetic parameters of venetoclax and ibrutinib will be determined at steady state using noncompartmental methods. The maximum observed plasma concentration (C_{max}), the time to C_{max} (peak time, T_{max}), the area-under-the-plasma concentration-time curve (AUC) over the dosing interval (AUC_{tau}) will be determined. Additional analyses may be performed as appropriate based on data availability.

4.0 Analysis Populations

The following population set will be used for the analyses:

The full analysis set (FAS) includes all subjects who received at least 1 dose of study drug. The FAS will be used for all efficacy (except the endpoints based on IRC assessment), safety, pharmacokinetic, and baseline analyses.

The per protocol (PP) population excludes FAS subjects who have been determined as having non-evaluable disease at baseline, based on IRC assessment. PP population will be used for IRC assessed endpoints. PP population will be used to compare the sensitivity of IRC endpoints with investigator assessed endpoints.

5.0 Subject Disposition

The total number of subjects who were screened, enrolled, and treated will be summarized. Reasons for exclusion, including screen failure, will be listed. Analysis for subject disposition will be based on FAS.

A summary of subject accountability will be provided where the number of subjects in each of the following categories will be summarized for each treatment group:

- Subjects enrolled in the study
- Subjects in each analysis population, FAS, and PP population.

- Subjects who discontinued study drug (venetoclax and ibrutinib) (all reasons and primary reason)
- Subjects who discontinued study.

6.0 Study Drug Duration and Compliance

For the FAS, duration of treatment will be summarized for each study drug (venetoclax/ibrutinib) and for venetoclax and ibrutinib combination. Duration of treatment is defined for each subject as last dose date minus first dose date +1. Duration of study drug (venetoclax/ibrutinib) and the combination will be summarized using the number of subjects treated, mean, standard deviation, median, minimum, and maximum. In addition, the number and percentage of subjects in each study drug and the combination duration interval will be summarized as below:

- 0 to 4 weeks
- > 4 weeks to 8 weeks
- > 8 weeks to 12 weeks
- > 12 weeks to 16 weeks
- > 16 weeks to 20 weeks
- > 20 weeks to 24 weeks
- > 24 weeks to 28 weeks
- > 28 weeks to 32 weeks
- > 32 weeks to 36 weeks
- > 36 weeks to 52 weeks
- 52 weeks

The number and percentage of subjects with dose reduction and dose interruption of venetoclax/ibrutinib will be summarized by the number of occurrences of dose reduction or interruption as no, 1 time, 2 times, or > 2 times.

Relative dose intensity (RDI) will be calculated for venetoclax/ibrutinib using observed dose intensity (ODI) and planned dose intensity (PDI):

- ODI: Actual total dose/ Actual total duration of treatment exposure (days)
- PDI:
 - PDI (mg/day) for venetoclax is calculated as the total amount of the planned dose (mg) during the maximum treatment period allowed (104 weeks) divided by the duration of the maximum treatment period allowed (104 weeks). Venetoclax started at 20 mg once daily and gradually ramped up to a target dose of 400 mg once daily over a 5-week period for a maximum period of 104 weeks.
 - PDI for Ibrutinib is based on fixed daily dosing of 560 mg/day.
- RDI (%) will be calculated as ODI/PDI *100 %.

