4 INVESTIGATIONAL PLAN

4.1 Overall Study Design and Plan

This Phase 2, open-label, single-arm study is designed to evaluate the efficacy and safety of the combination of venetoclax and ibrutinib in Japanese subjects with R/R MCL.

Approximately 12 subjects will receive ibrutinib at 560 mg once daily and venetoclax starting at 20 mg once daily and gradually ramped up to a target dose of 400 mg once daily over a 5 week period.

Dose-limiting toxicities will be evaluated in the first 6 subjects, from Day 1 for a minimum of 5 weeks and at least 1 week of venetoclax dosing at 400 mg, in order to confirm the initial safety and tolerability in Japanese subjects. After the completion of the DLT evaluation period in the first 6 subjects, the AbbVie Study Team and investigators who enrolled the 6 treated subjects will review all available safety and PK data to evaluate the tolerability of venetoclax in combination with ibrutinib in Japanese subjects with R/R MCL. If there are zero or 1 DLTs in the first 6 subjects, enrolment of the additional 6 subjects will proceed. If DLTs are observed in 2 or more of the first 6 subjects, further enrollment in Japan will be interrupted and additional, a detailed safety assessment will be conducted. The Sponsor will consult the Independent Safety Monitor (ISM) with results of the safety evaluation and Sponsor's conclusion on tolerability, then receive the answer from ISM.

To mitigate the risk of TLS, a ramp-up period of approximately 5 weeks will be employed with a stepwise increase of the venetoclax dose ([Figure 1](#)). Subjects will receive a venetoclax dose of 20 mg on Week 1 Day 1 of the ramp-up period and continue with dose increases every 7 days as tolerated. Ramp-up doses of venetoclax include 20 mg, 50 mg, 100 mg, 200 mg, and 400 mg. Subjects will receive ibrutinib at 560 mg once daily starting on Week 1 Day 1.

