If one or more electrolyte changes suggestive of TLS occur within 24 hours of the 20 mg dose, no additional venetoclax doses will be administered until resolution. If correction of electrolytes abnormalities is performed, the subsequent dose of venetoclax can only be given when electrolytes have been stable without any more treatment for at least 24 hours. Refer to [Table 2](#), Recommended Dose Modifications for Venetoclax-Related Toxicities, for additional TLS management guidelines. Upon resolution of laboratory abnormalities, the subject will resume at the ramp-up dose. When venetoclax dose interruptions are required during the ramp-up period, the next highest dose level may be initiated 7 days from the start of the current dose level, once the toxicity has resolved to Grade 1 or baseline level and at the investigator's discretion. At the investigator's discretion, the duration of a single dose level during the ramp-up period may be longer than 7 days before increasing to the next highest dose level.

For all ramp-up doses, laboratory values for subject management must be reviewed in real time by the investigator or designee, and prior to the subject's next dose, to ensure appropriate subject management. Based on the laboratory values, the subject may continue dosing, may need to hold dose until resolution, may require hospitalization for further monitoring, or may need additional post-dose laboratory checks.

Initially, subjects at high-risk for TLS will be hospitalized at the start of the venetoclax 20 mg ramp-up dose and again at the start of the 50 mg ramp-up dose for monitoring and prophylaxis of TLS. Subjects will be considered as high-risk for TLS if they have a high tumor burden (at least one lesion > 10 cm; or at least one lesion > 5 cm and circulating lymphocytes > 25,000 cells/mm³) and/or with baseline creatinine clearance (CrCl) < 60 mL/min. Subjects not meeting the high-risk criteria will be considered low risk for TLS. Subjects will be discharged from hospital if there is no evidence of TLS. AbbVie will review the safety data during the course of the study to determine whether continued hospitalization of subjects at high-risk for TLS during ramp-up remains warranted.

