9.0 Efficacy Analyses

9.1 General Considerations

PP population will be used for primary endpoint. PP population/FAS will be used for other efficacy endpoints, as appropriate.

All tests will be 1-sided at an alpha level of 0.025.

In the DLT assessment period, the first 6 study subjects enrolled was evaluated for the tolerability of the venetoclax and ibrutinib combination for a minimum of 5 weeks and at least 1 week of venetoclax dosing at 400 mg. DLT assessment committee along with ISM recommended that 'the study to be continued for full enrollment'.

The primary analysis will be performed after all subjects enrolled in the study have completed Week 13 disease assessment or have discontinued study, whichever is early.

The best overall response will be derived for each subject based on timepoint-wise disease assessments, according to the response categories ordered as CR > PR > SD > PD > NE (Not evaluable). Each subject will be assigned a "best overall response" based on the above-mentioned rule.

Unless otherwise specified, "Baseline" refers to the last non-missing observation before the first administration of study drug.

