13.0 Overall Type-I Error Control

The overall type I error rate of 1-sided 0.025 will be used to determine the statistical significance of the primary endpoint at the time of primary analysis. All other analyses will be done for descriptive purpose. Hence, no multiplicity adjustment of type I error is needed.

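### Venetoclax relative dose intensity compares a subject's own exposure with a 104-week planned average, so it understates dosing for any exposure shorter than 104 weeks

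*SAP*

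**What the plan says.** SAP Section 6.0 builds RDI from two averages. The first is the observed dose intensity, "ODI: Actual total dose/ Actual total duration of treatment exposure (days"), where duration is defined per subject as last dose date minus first dose date plus one. The second is the planned dose intensity. For venetoclax, "PDI (mg/day) for venetoclax is calculated as the total amount of the planned dose (mg) during the maximum treatment period allowed (104 weeks"). That total is then averaged over the full 104 weeks, the same for every subject. RDI is the ratio of the two as a percentage. For ibrutinib the planned value is a flat 560 mg/day.

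Protocol Section 4.1 gives the venetoclax schedule: "Ramp-up doses of venetoclax include 20 mg, 50 mg, 100 mg, 200 mg, and 400 mg", with increases every 7 days as tolerated. It also allows that "the duration of a single dose level during the ramp-up period may be longer than 7 days" at the investigator's discretion.

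On timing, SAP Section 9.1 states: "The primary analysis will be performed after all subjects enrolled in the study have completed Week 13 disease assessment", or have discontinued. On the status of the summary, SAP Section 13.0 says of everything other than the primary endpoint: "All other analyses will be done for descriptive purpose".

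**The concern.** The two averages in the venetoclax ratio cover different windows. The numerator covers the days the subject was on drug; the denominator covers 104 weeks whatever the subject's exposure. That would do no harm if the planned daily dose were constant, as it is for ibrutinib. For venetoclax the plan spends its first four weeks well below target. Those weeks are 4 of 104 in the planned average but 4 of 13 for a subject with 13 weeks of exposure.

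The section is headed as covering compliance, so readers will take RDI as a measure of how closely dosing followed the plan. If the measure falls simply because exposure is short, it mixes length of treatment with missed or reduced doses. With about 12 subjects, one or two short exposures can visibly move the summary. Early stops, where a reader most wants to know whether dosing had followed the plan, are distorted most.

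**Working it through.** The SAP prints no numerical PDI or RDI, so there is no stated figure to reproduce. The check applies the SAP's formula to the protocol's schedule.

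**Inputs.** Dose levels of 20, 50, 100, 200 and 400 mg and 7-day steps (Protocol 4.1); maximum of 104 weeks = 728 days, and the formulas for observed dose intensity (ODI), PDI and RDI (SAP 6.0). Assumption: exact 7-day steps, so 400 mg starts on Day 29.

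**PDI.** Ramp-up: 7 × (20 + 50 + 100 + 200) = 2,590 mg over 28 days. Remainder: 400 × 700 = 280,000 mg. PDI = 282,590 / 728 = 388.17 mg/day.

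**Fully adherent subject with T days of exposure (T ≥ 28).** ODI = [2,590 + 400 × (T − 28)] / T, and RDI = ODI / 388.17.

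| Exposure | ODI (mg/day) | RDI |
|---|---|---|
| 4 weeks | 92.5 | 23.8% |
| 5 weeks | 154.0 | 39.7% |
| 8 weeks | 246.25 | 63.4% |
| 10 weeks | 277.0 | 71.4% |
| 12 weeks | 297.5 | 76.6% |
| 13 weeks | (2,590 + 25,200) / 91 = 305.38 | 78.7% |
| 26 weeks | 352.69 | 90.9% |
| 52 weeks | 376.35 | 97.0% |
| 104 weeks | 388.17 | 100% |

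A day-by-day calculation gives RDI below 100% on every day from 1 to 727. This is general: the planned dose starts below target and never falls, so its mean over the first T days must be below its 728-day mean. The SAP's RDI equals the exposure-matched RDI multiplied by that ratio of means, at any level of adherence.

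**Sensitivity to the ramp-up assumption.** If 400 mg starts in Week 6 (200 mg for two weeks, in both plan and actual dosing), PDI = (3,990 + 400 × 693) / 728 = 281,190 / 728 = 386.25 mg/day. Fully adherent RDI is then:

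- 8 weeks: (3,990 + 400 × 21) / 56 = 221.25, giving 57.3%
- 13 weeks: (3,990 + 400 × 56) / 91 = 290.0, giving 75.1%
- 52 weeks: (3,990 + 400 × 329) / 364 = 372.5, giving 96.4%

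The size changes; the direction does not.

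**What the SAP's RDI cannot separate.** Compare three dosing histories:

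| History | SAP RDI | Exposure-matched RDI |
|---|---|---|
| Every dose taken, 13 weeks | 78.7% | 100% |
| 400 mg cut to 300 mg after Week 13, 26 weeks in all | (2,590 + 25,200 + 300 × 91) / 182 = 302.69, giving 78.0% | 302.69 / 352.69 = 85.8% |
| Same cut, 104 weeks in all | (2,590 + 25,200 + 300 × 637) / 728 = 300.67, giving 77.5% | 77.5% |

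The SAP's rule puts all three within about one point. The matched version separates them.

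**The case against.** The strongest reply is that nothing has been miscalculated. The SAP chose one reference intensity, and dose relative to the full-course planned mean is a readable quantity. Nowhere does the SAP promise that full adherence gives 100%. No decision rule uses RDI, the analysis is descriptive, and Section 6.0 also tabulates duration in eleven bands and counts reductions and interruptions, so RDI will not be read alone.

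The size can be contested too. Very large gaps arise only for early stops, and the documents do not say whether there were any. Protocol 6.3 suspends enrolment after the first 6 subjects for at least 5 weeks of DLT follow-up, so any of those 6 still on venetoclax would have about 17 to 18 weeks or more at the primary analysis. At 17 weeks a fully adherent subject has (2,590 + 400 × 91) / 119 = 327.65, or 84.4%. Finally, Protocol Appendix J says that the "primary analysis was completed and further IRC assessment will not be conducted", so that data cut has passed.

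Much of this stands as a limit on scope. It does not rescue the definition. In a section on compliance, a ratio of observed to planned dosing that cannot reach 100% before Week 104 will be misread. The companion tables help a reader guess the cause but leave the RDI figures uncorrected, and no other text truncates the PDI or excludes the ramp-up.

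One further point is fair but separate. Protocol 6.2 gives subjects with Child-Pugh class A at enrolment a 280 mg ibrutinib start, so perfect adherence would show as 280 / 560 = 50% against the flat PDI. That is a different mechanism and does not bear on the venetoclax formula.

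**Conclusion.** The concern holds. As written, the venetoclax RDI is biased downward for every exposure shorter than 104 weeks, by an amount that depends on length of exposure. Under full adherence and 7-day steps, the shortfall is:

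- about 29 to 76 points for stops at 10 down to 4 weeks (hypothetical, since the number of such stops is not given)
- about 21 to 23 points for the shortest ongoing exposure at the primary analysis, roughly 12 to 13 weeks, or about 25 points at 13 weeks if 400 mg starts in Week 6
- about 9 points at 26 weeks
- about 3 to 4 points at 52 weeks across the two ramp-up assumptions
- about 1 point at 78 weeks

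The direction does not depend on the step-length assumption; the exact figures do. The ibrutinib RDI does not carry this window mismatch, so the two drugs' RDIs in the same section are not comparable. The consequence is a misleading exposure summary and nothing beyond it.

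**What to change.** In SAP Section 6.0, define venetoclax PDI as the cumulative planned dose under the ramp-up schedule from Day 1 to the subject's last venetoclax dose day, or to the data cut for a subject still on drug, divided by that same number of days. Full adherence to the planned schedule then gives 100% at any length of exposure.

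State that the planned schedule uses 7-day steps. A longer step, which Protocol 4.1 permits, will still lower the corrected RDI. For one extra week at a single level, against the matched 13-week PDI of 305.38 mg/day:

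- at 20 mg: (2,730 + 400 × 56) / 91 = 276.15, giving 90.4%
- at 200 mg: 290.0 / 305.38 = 95.0%

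This point calls for no change to the ibrutinib definition.

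As the primary analysis is complete, apply the corrected definition to any further or final exposure reporting, and footnote the 104-week definition on any venetoclax RDI table already produced. The cost is one SAP sentence and a small programming change, with no new data, no change to dosing and no effect on the primary analysis.
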